7.4 Dosage Modification

Note: As the safety of the participant is paramount, the participants and their study partners will be told at the time of the informed consent that the study team will be monitoring their health and well-being through review of adverse events, laboratory results, and examinations performed during the trial. To help minimize the possibility of any unblinding of participants or study partners within any of these scenarios listed below, all participants will be informed at their time of consent that they may be asked to do one of three things if they are having adverse effects or abnormal laboratory results including: stopping treatment; receiving new, replacement syringes; or continuing treatment with the same syringes. Additionally, they will be told that the study team will continuously monitor their lab results, but they may not be told their specific results. Additionally, they will be informed that the trial physician or clinician designee will take the opportunity to examine them for clinical condition as a general safety measure if they are ever instructed to return to the CU-AMC site for an unscheduled visit.

The greatest safety concern noted with the investigational product is excessive leukocytosis. As advised by the product safety instructions, a CBC with differential, including examination for the presence of blast cells, will be competed twice weekly during the 24-week-long treatment phase. Additionally the product insert states that "If the ANC exceeds 20,000 cells/mm³ or if the platelet count exceeds 500,000/mm³, LEUKINE administration should be interrupted or the dose reduced by half. The decision to reduce the dose or interrupt treatment should be based on the clinical condition of the patient." If a participant has CBC with differential results which indicate that their ANC has exceeded 20,000 cells/mm³, their white blood cell count has exceeded 50,000 cells/mm³, or their platelet count has exceeded 500,000/mm³, the participant and the study partner will be immediately contacted, asked whether the participant is experiencing any adverse health effects, AND instructed NOT to administer any additional study product

injections. Whether the participant is experiencing any adverse health effects or not, treatments will be interrupted until the following steps are completed and the Principal Investigator or qualified medical designee has determined whether to resume treatments at full dosage (178.57 μ g/m²/day) or 50% reduced dosage (89.29 μ g/m²/day):

• If there are adverse health effects occurring, the participant and study partner will be instructed to immediately hang up and dial 911 if deemed an emergency or, if not deemed an emergency, to as quickly as possible return to the CU-AMC site to be examined by the trial physician or qualified clinician designee AND to bring all unused study product/syringes with them. (Note: At the time of initial contact with the participant and/or study partner, the trial personnel have the capability to immediately contact 911 emergency services if they believe the participant needs immediate attention.)

OR

[figure not shown]
- If there are not any adverse effects occurring (other than the blood value), the participant and study partner will be instructed to, as soon as possible, either return to the CU-AMC clinic or to a central contracted laboratory with phlebotomy services, whichever is quickest, to have an unscheduled blood draw performed "due to potentially abnormal or inconclusive lab results that need to be confirmed (exact phrasing may vary as deemed necessary by study personnel in their best attempts to prevent any un-blinding to the participant and study partner)." At this unscheduled visit to the CU-AMC site or central contracted laboratory, a follow-up CBC with differential will be performed and results obtained as quickly as possible.
- The ensuing steps will be followed pending results of this follow-up CBC with differential:
 - o If the results indicate that the ANC levels are now less than 20,000 cells/mm³, white blood cell count is less than 50,000 cells/mm³, and the platelet count is less than 500,000/mm³, and if determined appropriate by the trial's lead clinical sub-Investigator or delegated study clinician, the participant and study partner will be contacted and instructed to resume any additional study product injections and actions according to their regular daily scheduled times, **NOT** to administer any of the syringes that were missed during the days in which the unscheduled CBC with differential was performed and analyzed, if out of date, and to return any used AND unused syringes as normally done for each treatment week when they have their next study visit.

OR

O Although rarely expected based upon the experiences of the completed Leukine-AD trial (NCT01409915), the dosage may be reduced by half (i.e. 89.29 μg/m²/day subcutaneous injection) if the ANC exceeds 20,000 cells/mm³, the white blood cell count exceeds 50,000 cells/mm³, or the platelet count exceeds 500,000/mm³ in the most recent CBC, and if the trial's delegated sub-Investigator has determined, perhaps in consultation with a hematologist, oncologist or other qualified designee of the Sponsor, that the clinical condition of the participant warrants changing the dosage or continued interruption of treatment. If the results from the unscheduled follow-up CBC with differential has indicated that the ANC levels are still greater than 20,000 cells/mm³, and/or the white blood cell count is greater than 50,000 cells/mm³, and/or the platelet count is more than 500,000/mm³, the participant and the study partner will be immediately contacted again and instructed not to administer any additional study product injections AND to bring all unused and used study product/syringes to the clinic as soon as possible, so that they can

be assessed for clinical condition by a trial physician or qualified clinician designee AND to then potentially receive new syringes of the study product, which will be provided by the Research Pharmacy (prescribed by the lead clinical sub-Investigator) using procedures designed specifically for these types of unusual circumstances. In contacting and interacting with the study partner and participant for such a scenario, extreme care will be taken to not inadvertently unblind the participant, study partner, or any trial personnel. If unblinding is suspected, provisions described in prior section 7.3 will be followed and a decision will be made by the Sponsor regarding whether to discontinue the participant or to continue with the study.

Dosage Modification Flow Chart

In addition to these key blood values above, the responsible clinician will review the absolute eosinophil value, with a critical value, determined by the hematology specialist, set at $\geq 1.5 \times 10 E3/uL$ as a potential adverse event/clinically significant lab value. Management of this value will be as ongoing AE until the value returns to $< 1.5 \times 10 E3/uL$ and is evaluated by the responsible clinician as not clinically significant. Once the AE is resolved, a subsequent occurrence of an absolute eosinophil $\geq 1.5 \times 10 E3/uL$ will be classified as a new AE. For each new adverse event due to absolute eosinophil values, a symptom check will be conducted using guidelines developed by the hematology specialist. If they are free of symptoms, injections will continue on the regular schedule. If the participant is positive for any symptoms, they will be instructed to hold the injections pending further follow-up by the responsible sub-I. Within each ongoing AE, symptom checks will occur each time the participant's absolute eosinophil count is above the previous high value for that AE.

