Blood and CSF Biomarker Assessments (Continued)	an indication for treatment-related effects on blood brain barrier permeability and as a correlate with MRI analyses for any incidence of vasogenic edema or microhemorrhage. CSF and plasma will be assayed for A β (1-42), A β (1-40), t-tau, p-tau, tau:A β (1-42) ratios, NfL, GFAP, UCHL1, and panels of cytokines, chemokines, and other circulating factors to determine any treatment-related effects that might correlate with cognitive and activities of daily living changes.
	Serum Anti-Drug Antibody (ADA) Testing for Anti-GM-CSF Antibody will be assayed from serum collected by venipuncture blood draws at baseline, week 3, week 12, week 18, EOT, and follow-up visits.
	Apolipoprotein E (ApoE) Genetic Status will be determined via blood sample collected at Baseline visit.
Imaging Assessments	Fluorodeoxyglucose F18 (FDG) PET scan will be completed as part of baseline and EOT visit.
	MRIs of the brain will be conducted throughout the study period, including during screening period, week 6 visit, week 12 visit, week 18 visit, EOT visit, and at the follow-up visit.
	Amyloid PET utilizing an approved radiotracer (such as Vizamyl (flutemetamol F ¹⁸)) will be done as confirmation of elevated amyloid, or as an optional sub-study if LP is completed as confirmation. If participant consents, the PET will occur during Screening and at the follow-up visit.
Safety Assessments	Blood work including CBCs with differential and comprehensive metabolic panels (CMPs) will be collected at baseline visit, for the remainder of the treatment period, CBCs with differential twice a week and CMP once a week. At the End of Treatment Visit and follow-up visits, CBC with differential only. CBC will be repeated approximately 2 days and 9 days after last dose.
	Physical exams by study physician or qualified designee will be conducted at screening visit, Baseline, week 12, EOT, and follow-up visits.
	Electrocardiograms (ECGs) will be conducted at screening visit, week 12, and EOT visits.
	MRIs of the brain will be conducted throughout the study period, including during screening (Tier 2), week 6 visit, week 12 visit, week 18 visit, EOT visit, and at the follow-up visit.
	Vital signs and adverse events (AEs) will be monitored weekly.
	C-SSRS assessment of suicidality will be conducted at Screening, Baseline week 12 and EOT visits.

2 Schedule of Events

Schedule of Events - Screening Period	
Visit:	Screening Visit

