9.2 Data Analysis Plan

9.2.1 Primary Objective: To assess long-term tolerability and safety of sargramostim in individuals with mild-to-moderate Alzheimer's Disease

Generally, descriptive statistics will be utilized to examine safety of participants who received sargramostim injections compared to placebo injections. Safety will be assessed by measuring the toxicity grades of AEs. These toxicity grades have been standardized by the National Cancer Institute (NCI)

Common Toxicity Criteria for Adverse Events (CTCAE Version 5.00: November 27, 2017, attached as Appendix F). Differences in toxicity grades will be compared between treatments using a Wilcoxon test for ordered outcome. MRI scans will be assessed to identify ARIAs, including vasogenic edema and microhemorrhage. Additional safety assessments will include neurological and physical examinations, vital signs and suicidality evaluations. The current study will utilize a Data Safety Monitoring Board (DSMB) to review the clinical data and ensure participant safety within the parameters of the trial.

9.2.2 Secondary Objective: To test the hypothesis that sargramostim treatment, as compared to placebo, slows or halts cognitive decline or improves cognitive function in individuals with mild-to-moderate AD.

The foremost measure used for this secondary endpoint of assessing cognitive function will be the MMSE, as it has been reported to be most sensitive to cognitive changes over time due to treatments in people ranging from late mild cognitive impairment to AD in clinical trials up to 2 years in length ¹²⁴. The cognitive assessment will be based on the participants' MMSE total score changes from Baseline to End of Treatment.

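### Section 7.4 adds symptom enquiries triggered by blood counts, with no counterpart for untriggered participants, so symptomatic AEs may be over-recorded on sargramostim by an amount the protocol does not let one estimate

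*Protocol*

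**What the plan says.** Routine ascertainment does not depend on arm. The synopsis states "Vital signs and adverse events (AEs) will be monitored weekly", and the Schedule of Events marks AE review at Baseline, weeks 2 to 24, EOT and follow-up. CBCs with differential are taken twice weekly in everyone.

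Section 7.4 adds enquiries that depend on those counts:

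- **Eosinophils.** A value of 1.5 x10E3/uL or more is handled as a potential AE. For each new one, "a symptom check will be conducted using guidelines developed by the hematology specialist". Within an ongoing episode, "symptom checks will occur each time the participant's absolute eosinophil count is above the previous high value for that AE".
- **High counts.** If ANC exceeds 20,000, white cells 50,000 or platelets 500,000 per mm³, participant and study partner "will be immediately contacted, asked whether the participant is experiencing any adverse health effects". An examination follows if there are symptoms or the excess persists.

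Section 8.4.5 records any new condition or event after consent as an AE, so symptoms found at these contacts enter the AE data. Section 9.2.1 is largely descriptive but names one test: "Differences in toxicity grades will be compared between treatments using a Wilcoxon test for ordered outcome".

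**The concern.** The triggers are outcomes measured after randomisation, and some are outcomes the drug is given to change. Section 4.5 puts white-cell mobilization in the primary endpoint, and section 7.4 says "The greatest safety concern noted with the investigational product is excessive leukocytosis". If sargramostim participants cross the thresholds more often, they are asked about symptoms more often. Nothing in the protocol gives an equivalent enquiry to a participant whose counts stay low. The consent wording in section 7.4 protects the blind but does not equalise enquiry.

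Mild symptoms that would go unreported without a trigger could then be recorded more often on sargramostim. The grade comparison would mix drug effect with intensity of enquiry. With about 28 and 14 participants, a few extra mild events can alter the picture for the primary objective.

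**Working it through.** The protocol gives no figure on this point to reproduce. The check has three parts.

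**1. Common ground between arms.** Scheduled AE contacts from the Schedule of Events: 1 (Baseline) + 23 (weeks 2–24) + 1 (EOT) + 1 (follow-up) = 26 per participant. CBCs: 2 × 24 = 48 per participant. Both are the same in each arm, so any asymmetry comes only from the triggered contacts.

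**2. Where triggered participants would fall.** Section 9.1 gives 28 sargramostim and 14 placebo. With r the ratio of trigger rates (sargramostim to placebo), the sargramostim share of triggered participants is 28r/(28r + 14):

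- r = 1: 28/42 = 67%, from allocation alone
- r = 2: 56/70 = 80%
- r = 4.5: 126/140 = 90%
- r = 9.5: 266/280 = 95%

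The protocol gives no value of r.

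**3. Effect on the comparison when the drug causes no symptoms.** All inputs here except the 28 and 14 are assumptions. Symptom episodes per participant are Poisson with mean 1.5 in both arms. Grades 1/2/3 occur in 70/25/5%, and grade 3 is always recorded. Other episodes are recorded with probability b under routine review, and e in a participant who triggers. Triggers occur in 2% of placebo participants (0% in the first row). The test is a two-sided Wilcoxon rank-sum on worst grade at 0.05, with 3,000 runs per cell.

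Proportion of trials rejecting:

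| Triggers, sargramostim v placebo | b 0.80, e 0.95 | b 0.60, e 0.90 | b 0.40, e 0.90 |
|---|---|---|---|
| 0% v 0% | 0.043 | 0.040 | 0.046 |
| 20% v 2% | 0.042 | 0.052 | 0.052 |
| 50% v 2% | 0.052 | 0.068 | 0.114 |
| 80% v 2% | 0.056 | 0.096 | 0.219 |

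Simulation error near 0.05 is √(0.05 × 0.95/3000) = 0.004.

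Participants with any recorded symptomatic AE at 50% v 2%, sargramostim v placebo: 73% v 71%, 68% v 60% and 61% v 48% across the three columns.

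The middle pair can be checked by hand. An episode is recorded with probability 0.95 × 0.60 + 0.05 = 0.62 if untriggered and 0.95 × 0.90 + 0.05 = 0.905 if triggered. The chance of any recorded episode is 1 − exp(−1.5 × 0.62) = 0.605 and 1 − exp(−1.5 × 0.905) = 0.743. Sargramostim: 0.5 × 0.743 + 0.5 × 0.605 = 0.674. Placebo: 0.02 × 0.743 + 0.98 × 0.605 = 0.608.

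The model favours the concern in one respect: in a triggered participant every episode over the trial gets the higher detection probability, whereas a real check would reach only symptoms present around that time.

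**The case against.** The rules apply to everyone by count, not by arm, and weekly review is common to both arms, so a triggered check will often only bring forward a report due within days. That stands, and it limits the gap.

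A reader might infer that the extra enquiries fall almost only on sargramostim. The documents do not support this. It needs a rate ratio of about 4.5 or more, and no rate is given. No section says the drug raises eosinophils, and section 8.4.5.3 lists excessive white-cell increase among the less common effects. On halving the dose for high counts, section 7.4 says "Although rarely expected based upon the experiences of the completed Leukine-AD trial". That remark has limited weight: it concerns dose halving, and the earlier trial gave 15 doses over 19 days against up to 168 here.

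A reader might also infer that triggered checks are more searching than weekly review. The content of the specialist's guidelines is not shown, the high-count call is an open question, and the weekly questions are not described. Weak routine detection is plausible, since participants have MoCA 4–24 and the informant need be present only 12 hours a week, but it is not documented.

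Nor can one say the problem could never be repaired afterwards. The full AE form is not shown, count results should be dated, and section 7.5 requires interruptions to be documented, so partial reconstruction may be possible. Analysis details may properly sit in the SAP. The unequal enquiry, however, is set by the protocol's own collection rule.

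Finally, direction in the test depends on the unit. On worst grade per participant the bias runs against sargramostim. If individual events were ranked, extra mild events would lower that arm's grade distribution. Section 9.2.1 does not state the unit.

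**Conclusion.** The concern holds as a possible ascertainment bias of unknown size. The mechanism is in the text: count-triggered enquiry, no matching enquiry without a trigger, findings entered as AEs, and grades compared between arms. The expected direction for the number of recorded symptomatic AEs is upward on sargramostim. This assumes white-cell triggers are more frequent there, which follows from the drug's action but is not quantified.

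On the assumed inputs the effect is negligible when triggers are rare (rejection 0.042–0.052 at 20% v 2%). It stays small when weekly review is sensitive (0.056 at most with routine detection of 0.80). It becomes material only when triggers are common and routine detection is weak (0.114 to 0.219 in the right-hand column at 50% and 80%). The documents do not show which case applies, so a reader should not conclude that the safety comparison is invalid. The point merits a cheap precaution at the data-collection stage.

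**What to change.** Leave the triggered checks and every clinical action in section 7.4 as they are. Then:

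1. Ask the same symptom questions at the weekly AE review already scheduled for every participant in both arms.
2. Add a field to the AE form for how the event was found: scheduled review or result-triggered contact.
3. In section 9.2.1, keep AEs from all sources as the main between-arm comparison, and add a sensitivity comparison that excludes AEs found only at result-triggered contacts. The order matters: making the restricted set the main comparison would drop genuine symptoms that accompany drug-induced count rises and could understate harm.

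The cost is a few minutes per weekly visit, one form field and a sentence in section 9.2.1. The downside is somewhat more mild AEs recorded in both arms.

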7.5 Interruption of Treatment

Temporary interruption of treatment is allowed if a short-term treatment with an excluded medication is necessary, secondary to hospitalization, personal circumstances, or to evaluate the study drug impact on an uncertain AE, including but not limited to abnormal CBC with differential results (see Section 7.4), Grade 2 or higher AEs, and Grade 2 or higher abnormal laboratory values. Interruption of treatment should only be limited to significant events. If temporary interruption is due to an AE, it will be reported to the DSMB as part of the regularly scheduled aggregate reports. In such cases as above, reinitiation of treatment is at the trial physician(s) or qualified delegated clinician(s) judgement.

If a participant has to interrupt treatment for an extended period of time due to a significant medical condition or life event (such as greater than 7 dosing days off drug), it is possible to re-initiate treatment, and restarting the treatment will be at the trial physician's discretion, though it is suggested that if deemed necessary, consultation with the Sponsor may be done. Treatment re-initiation should occur as soon as possible and has to be confirmed by trial physician. Re-initiation of treatment will include a general safety examination by qualified medical personnel and safety labs. Restarting treatment after an interruption period that is greater than 10% of the trial length (i.e. 18 consecutive days) will be discussed between sponsor and trial physician before a final decision is made to re-initiate treatment at the discretion of the Sponsor. All information relating to interruption of treatment and re-initiation will be documented. Missed doses from the above category will not be considered in determining non-compliance.

7.5.1 Interruption of Treatment not related to short term treatment with excluded medication, hospitalization, personal circumstance or AE.

At the discretion of Principal Investigator, participants may request an interruption of treatment due to commitments such as travel obligations, for one block of time, up to 4 weeks in duration (28 dosage days). The study recording of interruption of treatment will allow for the addition of the time taken off to the study treatment period, up to the predetermined 28 dosage days. This interruption will not be factored into non-compliance, and a safety examination by study clinician is not required prior to resuming treatment.

7.6 Treatment Compliance

Compliance will be assessed at study visits via participant diary when the materials are returned at each weekly study visit at the clinic or by the traveling nurse if the weekly visit occurs at home. When possible, clinic injections will be performed by caregivers with delegated study staff observation for confirmation of correct injection technique. Ongoing injection technique education will be provided as needed. Delegated study staff will perform clinic injections as needed at visits if caregivers are unable to administer the investigational product or placebo. Non-compliance is generally defined as a willful disregard for following the treatment plan by the participant or study partner).

Only participants who use 90% (151 out of 168 administration days) of the prescribed daily dosage will be considered compliant (missed doses due to circumstances described in Sections 7.5 and 7.5.1 are not factored into treatment compliance). Participants deemed non-compliant may be, at the discretion of the

investigator, in consultation with the Sponsor, discontinued from the study. If a participant is deemed non-compliant within the first 3 weeks of the trial, a discussion at the next in-person clinical visit or via phone prior to or during the next in-person visit with the PI or sub-I or other delegated study staff and retraining on treatment administration and compliance will occur to attempt to increase compliance.

As stated above, reduction in dosage (i.e. reduction from 178.57 $\mu g/m^2/day$ to 89.29 $\mu g/m^2/day$) OR doses withheld due to AEs or other factors relevant, as determined and approved by the PI, and Sponsor, will not be factored into non-compliance of a participant.

